10.1.5 Physical Exam

Physical examinations will be conducted within 21 days for eligibility assessment prior to randomization. An important component of the physical exam is the accurate measurement of height (in cm) and weight (in kg). All pertinent findings will be recorded on the appropriate pages of the CRF. All changes relative to baseline considered to be clinically significant by the Investigator will be reported as AE's and recorded in the CRF.

The physical exam must be conducted at the following times:

- Once within 21 days of RFA treatment (initial and any re-treatment).
- Post RFA prior to discharge.
- Day 14 (+/- 3 days)
- Day 28 (+/- 3 days)
- Month 5, Month 9, Month 13 (+/- 2 weeks) or disease progression, whichever occurs first
- Day 7 (+/- 3 days) for subjects with elevated bilirubin

10.1.6 Vital Signs

Vital signs, which include temperature (in Celsius), blood pressure, pulse rate, and respiration must be obtained. Vital signs must be collected in a position that is consistent for all time points for each subject and will be collected at the following times:

- Once within 21 days of RFA treatment (initial and any retreatment)
- Before administration of the investigational product. Note: subjects with a temperature or blood pressure outside the eligibility criteria at the pre-dose evaluation should NOT receive treatment with investigational product.
- Within 15 minutes after completing study drug infusion and after RFA completion at 30 minutes (+/- 15 minutes), 1 hour (+/- 15 minutes), every 2 hours (+/- 15 minutes) until the subject is stable or discharged.
- Day 14 (+/- 3 days)
- Day 28 (+/- 3 days)
- Month 5, Month 9, Month 13 (+/- 2 weeks) or disease progression, whichever occurs first
- Day 7 (+/- 3 days) for subjects with elevated bilirubin

10.1.7 ECOG Performance Status

The Investigator will evaluate the patient's ECOG performance status within 21 days prior to study treatment.

10.1.8 Imaging

CT or MRI scans (Chest, Abdomen and Pelvis) will be done within 21 days prior to study treatment to confirm the presence of an evaluable lesion and at Day 28 to assess whether a complete initial ablation was achieved. Additional imaging will be done at months 5, 9, 13, 17, 21, 25, then every 6 months (+/- 2 weeks) until disease progression is seen. The following requirements apply to imaging for this study:

- The same modality and technique must be used for all scans of an individual patient.
- Investigator-determined radiological progression must be documented prior to any non-study HCC treatment. Imaging follow-up should continue for subjects with clinical evidence of progression until radiological disease progression is confirmed before beginning any non-study cancer treatment.
- The date of progression will be reported to the CRF.

Once the PFS endpoint is met, no further CT and MRI scans are required for this study.

For subjects with incomplete ablations who are re-treated a second time and complete ablation is achieved, the imaging studies will continue per protocol with Day 0 set as the date of the second ablation procedure. If the lesion cannot be completely ablated after the second treatment, then the subject will be considered a treatment failure. Such subjects will continue to be followed for adverse events through Day 28 following the re-treatment; they will also continue to be followed for OS every 3 months.

10.1.9 ECG

Acquire an ECG (12 lead with paper printout) at the following time points in relation to study drug treatment:

Pre-Treatment

- Within 21 days prior to study drug infusion

Post-Treatment

- Once subject is stable after RFA procedure
- Day 28 (+/- 3 days)
- Month 5, Month 9, Month 13 (+/- 2 weeks) or disease progression, whichever occurs first

The Investigator will comment on any changes considered to be clinically significant and report as an AE. All changes considered clinically significant after Day 28 should be reported as AEs and recorded in the CRF if considered possibly, probably or definitely related.

10.1.10 ECHO/MUGA Scan for LVEF Monitoring

A baseline echocardiogram (ECHO) must be carried out within 21 days prior to study treatment. Measurements with a MUGA scan are allowed if an echocardiogram cannot be performed; however, the same modality used at baseline must be used for follow-up. Follow-up scans must be completed on Day 28 (+/- 3 days) and at Month 13 or at time progression of disease, whichever occurs first.

A decrease of >10% in resting LVEF that becomes abnormal (lower than the institutional lower limit of normal) should be further evaluated by repeat examination for subjects with a total cumulative doxorubicin of $\geq 300 \text{ mg/m}^2$.

10.1.11 Serum Pregnancy Test

Women of child bearing potential must undergo a serum pregnancy test within 21 days prior to each administration of study drug.

10.1.12 Laboratory Analytes

Table 2: Laboratory Analytes

Hematology	Clinical Chemistry		Urinalysis
Hematocrit	Sodium	AST/SGOT	pH
Hemoglobin	Potassium	ALT/SGPT	specific gravity
RBC count	Chloride	Alkaline Phosphatase	Protein
WBC count	Glucose	Total protein	Glucose
Differential WBC count	Urea nitrogen	Albumin	Ketones
Platelets	Creatinine	Calcium	Blood
PT	Total bilirubin	AFP	WBC/HPF
INR			RBC/HPF
			Crystals

The laboratory will perform evaluations of the analytes listed in Table 2 above. Evaluations should take place as follows:

- Within 21 days prior to study drug infusion- Repeat laboratory analysis is permitted to evaluate eligibility prior to treatment. The repeat analysis results must meet the eligibility criteria prior to study drug infusion.
- Day 14 (+/- 3 days)
- Day 28 (+/- 3 days)
- Day 7 (+/- 3 days) for subjects with elevated bilirubin

Additional hematologic tests (CBC with differential) will be collected at months 5, 9, and 13 or disease progression, whichever occurs first.

Additional post-treatment liver function tests (Chemistry and PT/INR), will be collected at months 5, 9, 13, 17, 21, and 25 (+/- 2 weeks) or disease progression, whichever occurs first.

10.2 Re-Treatment

A subject who has an incomplete initial ablation is eligible for 1 retreatment procedure within 21 days after the scan showing residual disease at Day 28. Subjects will be retreated only once with the same treatment assigned at randomization. Baseline safety evaluations must meet the eligibility parameters prior to a retreatment. The second ablation must occur no later than 21 days after the first post-ablation scan assessment at Day 28. Such subjects will continue to be followed for AEs/SAEs through Day 28 after the second study drug administration. Subjects with a complete ablation after retreatment will be followed for all primary and secondary endpoints. If after 2 ablations the subject has local, distant intrahepatic, or extrahepatic HCC, then the subject will be considered a treatment failure and will have met the PFS endpoint. The subject will still be followed for OS.

Among subjects who are not treatment failures, five repeat treatments may be permitted to treat a recurrent lesion or to treat newly-identified local or distant intrahepatic lesions at the Investigator's discretion after the PFS endpoint is reported and with agreement from the Sponsor. The subject must be eligible for retreatment consistent with the safety eligibility criteria and will be retreated with the same randomized treatment.

Subjects who develop extrahepatic lesions will have met the PFS endpoint and are no longer eligible for further protocol treatment; they will be followed for OS.

10.3 Unscheduled Assessments and Early Discontinuation

The Investigator may, at his or her discretion, arrange for a subject to have an unscheduled assessment(s), especially in the case of adverse events that require follow-up. If the subject is experiencing an adverse event considered by the Investigator to be possibly related to the use of study treatment, then an unscheduled visit should be performed.

If the subject is discontinued from participation within the first year for any reason, the Investigator must make every effort to perform Month 13 evaluations as described in Table 1.

11. CONCOMITANT MEDICATIONS

Subjects may take any medication that is not restricted by the protocol and would not be expected to interfere with the intent and conduct of the study. Chronic medications should be dosed on a stable regimen, if possible. In the case of medications restricted by the protocol, adequate washout times must be observed. Please reference Appendix III for an explanation of washout times. All medications (including herbal preparations) at the time of screening and within 30 days prior to study drug treatment and other treatments taken by the subject during the study and up to 24 hours following treatment, including those treatments initiated prior to the start of the study (ICF signing), must be recorded on the Case Report Form.

Subjects should receive full supportive care during the study, including transfusion of blood and blood products, and treatment with antibiotics, antiemetics, antidiarrheals and analgesics, as appropriate.

Supportive medications may be administered during the course of study for toxicity at the discretion of the Investigator. Subjects with myelosuppression may require blood or platelet transfusions, filgrastim (or other colony stimulating factors), or other supportive care medications, all of which may be administered at the Investigator's discretion. Antiemetics may be administered to control nausea and vomiting, and antidiarrheals may be prescribed for diarrhea.

Liposomal drugs (AbelectTM, AmbisomeTM, NyotranTM, etc.), or lipid-complexed drugs (fentanyl, etc.) or intravenous fat emulsions could change the pharmacokinetic profile of ThermoDox and should not be administered to study subjects while on the trial. Intravenous fat emulsions, except propofol, should be prohibited as instructed in Appendix III.

Doxorubicin is a substrate of CYP3A4. The following medications are prohibited from the specified time-point before the first dose of study drug treatment:

- Other anti-cancer therapy should not be given until Investigator determined radiological disease progression, at minimum 30 days after the last study treatment, or withdrawal from the study. Subjects who receive concurrent anti-cancer therapy will be discontinued from the study.
- Any other investigational drugs, from 30 days or 5 half-lives, whichever is longer, prior to the first dose of study treatment until Investigator determined radiological progression. Subjects should not start another investigational drug without discussion with the medical monitor. If an investigational drug is initiated, it must be a minimum of 30 days after the last study drug treatment (except in re-treatment)

- Inducers and inhibitors of CYP3A4 – these may alter the metabolism of ThermoDox, as the drug is a substrate for CYP3A4. CYP3A4 inducers and inhibitors that are prohibited from screening through 30 days after the last study treatment can be found in Appendix III Prohibited Medications;
- Certain herbal supplements are prohibited as listed in Appendix III.

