7.2 Subject Discontinuation

Subjects will be discontinued from the study if they withdraw consent.

Following progression, sites are instructed to contact subjects at 3-months intervals. At each follow-up interval, if contact cannot be made on the first attempt, then the site MUST document 3 attempts to contact the subject using phone calls or visits to the physician's offices. If the site is unable to contact the subject, then a "certified or tracking letter" MUST be sent to the subject's last known residence. This method of contact should be attempted at 3 consecutive follow-up intervals prior to the subject being considered lost to follow up.

If a subject discontinues from retreatments or from the PFS imaging interval, the patient should still be contacted for overall survival until withdraw consent for study participation.

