7.3 Study Noncompliance

All instances of noncompliance and all significant protocol violations will be reported to the appropriate ethics committee per local regulations. All instances of eligibility violations or deviations will be recorded on the case report forms and reported to Sponsor.

If a subject is discontinued from the study due to noncompliance of follow up visits, the patient should still be contacted for overall survival until end of study or withdraw consent from study participation.

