8.5 Dose Modifications

8.5.1 Hepatobiliary Surveillance

Subjects with an elevated serum bilirubin level (> 2.0 and ≤ 3.0 mg/dL) at baseline will have additional safety assessments at Day 7 post-ablation and at any other time the physician deems it necessary. These assessments should include a physical exam, vital sign, AE and concomitant medications assessment, and a CBC, UA and chemistry laboratory draw. Grade 3 – 4 hepatic toxicities are to be followed until resolution.

No dose modification is required for patients with elevated serum bilirubin.

8.5.2 Suggested Management for Hypersensitivity Reactions:

Severity of Symptoms:	Treatment Guidelines:
Mild Symptoms: localized cutaneous reactions such as mild pruritis, mild flushing, and mild rash. (Grades 0-1)	
Consider decreasing the rate of infusion until recovery from symptoms, stay at bedside and monitor subject.Then, complete study drug infusion at the initial planned rate.
Moderate to Severe Symptoms: any symptom that is not mild (see above) such as generalized pruritis, generalized flushing, generalized rash, dyspnea, hypotension with systolic BP < 80 mm Hg, bronchospasm, angioedema and generalized angioedema. (Grades 2-4)	
Stop infusion.WITHDRAW FROM STUDY TREATMENT
Anaphylaxis (Any degree of anaphylaxis): (Grade 4)	
Stop infusion.WITHDRAW FROM STUDY TREATMENT

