8.5.4 Dose Modification for Re-Treatment ONLY

Among patients requiring re-treatment after incomplete initial ablation who have developed Grade 4 hematologic toxicities, the absolute neutrophil and platelet counts must return to less than or equal to grade 1 before re-treatment.

The investigator should follow local/institutional cytokine support or in the absence of local guidelines for cytokine support, the investigator may use the “American Society of Clinical Oncology 2006 Update of recommendations for the use of white blood cell growth factors: An Evidence-Based Clinical Practice Guideline” (Smith et al. 2006). The second ablation must occur no later than 21 days after the first post-ablation radiographical imaging assessment at Day 28. If the patient does not meet the dose modification criteria within the timeframe, then patient should be taken off study and treated as clinically necessary.

HEMATOLOGICAL TOXICITY*			
GRADE	ANC	PLATELETS	MODIFICATION
1	1500-1900	75,000-150,000	Resume treatment with no dose reduction
2	1000-<1500	50,000-<75,000	Wait until ANC \geq 1,500 and platelets \geq 75,000; redose with no dose reduction
3	500-<999	25,000-<50,000	Wait until ANC \geq 1,500 and platelets \geq 75,000; redose with no dose reduction
4	<500	<25,000	Wait until ANC \geq 1,500 and platelets \geq 75,000; redose at 25% dose reduction or continue full dose with cytokine support

*Dose reduction guidelines to investigators for subjects who experience Grade 4 absolute neutrophil counts (ANC) or Grade 4 platelet count and require additional ablation due to incomplete ablation

Among patients requiring re-treatment after incomplete initial ablation who have developed a non-hematologic toxicity \geq grade 3, no dose modification is required. Instead, such subjects will not be re-treated until the severity of the non-hematologic toxicity drops to \leq grade 2.

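### Two exit rules (protocol sections 8.5.4 and 11) take subjects off the study without saying that survival contact continues, and they are not reconciled with section 7.2

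*Protocol*

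**What the plan says.** **The two exit rules.** Protocol section 11: "Subjects who receive concurrent anti-cancer therapy will be discontinued from the study". Protocol section 8.5.4, on a subject who does not meet the re-treatment criteria within the permitted window: "then patient should be taken off study and treated as clinically necessary". Neither section mentions survival contact.

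**The general rule.** Section 7.2: "Subjects will be discontinued from the study if they withdraw consent". The same section adds: "If a subject discontinues from retreatments or from the PFS imaging interval, the patient should still be contacted for overall survival", and keeps that contact going until consent is withdrawn.

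**Where the protocol is explicit.**
- Section 7.3: "If a subject is discontinued from the study due to noncompliance of follow up visits, the patient should still be contacted for overall survival".
- Section 10.1.8, on treatment failures: "they will also continue to be followed for OS every 3 months".
- Section 10.2, on the same group: "The subject will still be followed for OS".
- The hypersensitivity table in section 8.5.2, where only treatment stops: "WITHDRAW FROM STUDY TREATMENT".

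**Survival checks.** Section 12.1 (repeated in SAP section 4) confirms survival at each imaging visit, every 4 months to month 25 and every 6 months after that, until progression. Section 5.1 and footnote 15 of Table 1 set contact every 3 months after radiological progression.

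**Censoring.** Protocol section 15.2.1 and SAP section 3 censor OS at the last study follow-up or the cut-off date, whichever is earlier.

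**The concern.** OS in all randomised subjects is the primary endpoint, so a subject who stops treatment or imaging should still be traced for vital status. Sections 8.5.4 and 11 use terms that mean leaving the study, for reasons other than withdrawn consent, and do not say that tracing goes on. The protocol elsewhere states continued OS contact when it wants it, and writes withdrawal from treatment when that is all it means. A site could therefore take the silence as a full exit.

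The moment of exit is unlikely to be neutral. A subject under section 8.5.4 has residual tumour and no second ablation. A subject under section 11 has received other anti-cancer therapy. Both are plausibly related to prognosis, so censoring OS there could be informative.

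**Working it through.** **1. The passages side by side**

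| Situation | Protocol section | OS contact stated? | Interval stated? |
|---|---|---|---|
| Stops re-treatment or PFS imaging | 7.2 | Yes | No |
| Discontinued for missed visits | 7.3 | Yes | No |
| Treatment failure after two ablations | 5.1, 10.1.8, 10.2 | Yes | 3 months (5.1, 10.1.8) |
| After radiological progression | 5.1, Table 1 | Yes | 3 months |
| Still being imaged | 12.1 | Yes | 4, then 6 months |
| Re-treatment criteria not met in time | 8.5.4 | No | No |
| Concurrent anti-cancer therapy | 11 | No | No |

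**2. Who falls in the gap**

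A subject under section 8.5.4 has had one ablation. Treatment failure needs two (sections 12.4 and 15.2.2.1), so the 3-monthly rule for failures does not clearly apply. A subject under section 11 may have no recorded progression, so the post-progression contact need not have started; the section does not define concurrent. The section 7.2 procedure of repeated attempts and a tracked letter is written for the period after progression. Section 10.3 asks for the Month 13 evaluations if a subject is discontinued in the first year. The section 8.5.4 window closes at about day 28 + 21 = 49, so section 10.3 applies to that group, but it sets nothing after Month 13.

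**3. The plan's own figure**

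Inputs from section 15.4.1: HR 0.67, one-sided 0.025, 80% power, 1:1 allocation.

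Deaths = 4 × (1.960 + 0.842)² / (ln 0.67)² = 195.8, so 196, against 197 stated. The design reproduces, and this point does not alter the event target.

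**4. Balanced loss: delay only**

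Inputs: 550 subjects, control median 54 months, HR 0.67 and 3% loss per year (section 15.4.1); 36 months of accrual (synopsis, taken as uniform). Survival is taken as exponential.

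- Control hazard h = ln 2 / 54 = 0.01284 per month; ThermoDox hazard 0.67 × 0.01284 = 0.00860.
- Loss rate η = −ln(0.97)/12 = 0.00254 per month.
- Chance of an observed death within T months = h/(h+η) × [1 − exp(−(h+η)T)], averaged over entry times.

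With no extra loss, the 197th death falls 27.3 months after the last randomisation, close to the plan's approximate 30. The share removed below is an assumption, with last contact at month 2 and equal shares in both arms.

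| Share removed | 197th death (months) | Delay (months) |
|---|---|---|
| 2% | 28.5 | 1.2 |
| 5% | 30.4 | 3.1 |
| 10% | 34.0 | 6.7 |

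**5. Loss that differs by arm: illustration only**

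For scale, section 6.2.4 reports 291 of 343 ThermoDox subjects in the prior trial with a single dose. So 343 − 291 = 52 (15.2%) had more, which is about 275 × 52/343 = 42 subjects here. This is a guide and not a bound, because a subject removed under section 8.5.4 would count as single-dose. Suppose a number equal to 20% of those 42, about 8 or 3.0% of the ThermoDox arm, lost contact in that arm only, and had 2 to 3 times the hazard of other subjects. Simulated with a true HR of 1.00, an unstratified log-rank test and a single look at 197 deaths:

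- Last contact at months 1 to 2: estimated HR 0.96 to 0.98, one-sided error about 0.035 to 0.045.
- Last contact at Month 13, as section 10.3 would give: HR 0.98 to 0.99, error about 0.030 to 0.033.
- The same 3.0% lost in both arms: HR 1.00, error close to 0.025.

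Control-only loss works the other way. With 5% removed under section 11 in the control arm alone, the HR is 1.02 to 1.04, against ThermoDox.

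**The case against.** The strongest reply is that the protocol, taken whole, keeps these subjects.

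- Section 7.2 does not say that withdrawn consent is the only ground for discontinuation, and section 7.3 supplies another.
- The section 7.2 clause on re-treatment and imaging can be read to cover a subject whose re-treatment never happens, or who leaves imaging after other therapy.
- Section 7.3 shows that being discontinued from the study need not end contact.
- Section 12.1 monitors all patients for survival, and section 7.4 continues survival follow-up for 5 years after the last randomisation.
- SAP section 3 censors PFS, not OS, for non-study therapy. SAP section 6.2.7 tabulates subjects who start such therapy without documented progression, and a sensitivity analysis in SAP section 6.3.3 counts deaths up to the survival cut-off.

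Most of this stands, and it sets the limits of the point. A reader might infer that OS follow-up ends for these subjects by design; the documents do not say so. A reader might also infer that no survival check exists before progression. That is wrong, because section 12.1 sets one for everyone still being imaged.

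What remains is that sections 8.5.4 and 11 are instructions a site acts on, they carry no OS clause, and the section 7.2 fallback gives no interval and does not clearly reach a subject discontinued under section 11.

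**Conclusion.** The point holds as an unreconciled conflict between stated rules, and it should be fixed. It does not show that OS data will be lost. The gap is confined to subjects who leave imaging, or are taken off study, without recorded progression and who are not treatment failures.

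The effect is probably small. No passage gives a removal rate, a prognosis for those removed, or a split by arm, so neither size nor direction can be derived. A reader might take the simulated error rates as evidence of an inflated type I error. They are not: they need removal concentrated in the ThermoDox arm, an assumed 2- to 3-fold hazard and an assumed rate, and they shrink if the Month 13 evaluations are done. An arm difference is plausible only under section 8.5.4, because myelosuppression is a main doxorubicin toxicity (section 6.2.4), and section 3.3 describes the neutropenia and leukopenia in the prior trial as reversible. Confidence is medium, mainly because site practice may already follow the probable intent.

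**What to change.** 1. In sections 8.5.4 and 11, state that the subject leaves study treatment and, where applicable, PFS imaging, but remains in OS follow-up until death, withdrawal of consent or the end of the study. Each section should say which of treatment and imaging stops. This reconciles both with section 7.2.
2. State a vital-status interval for subjects who leave imaging before recorded progression. The 3-month interval already used after progression is one option. Extend the section 7.2 contact-attempt procedure to them.
3. Optionally, add a sentence to SAP section 3 that OS is not censored for non-study therapy or for stopping study treatment. The current OS rule already implies this.

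The cost is one clause in each of two sections, a line on the interval and contact procedure, and a few extra vital-status contacts. No treatment or dosing rule, event target or test changes.
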